Statistical Analysis Plan Document Cover Page

Official Title of the Study: Trial of Self-managed Approaches for Patellofemoral Pain Syndrome in Active Duty Military

NCT Number: NCT02597673

Date of Document: July 16, 2015

Trial of Self-managed Approaches for Patellofemoral Pain Syndrome (PFPS) in Active Duty Military

Statistical Analysis Plan for PFPS Study

Data Analysis: The primary goal of the analysis is to compare changes over time in the three treatment groups and a usual care control group.

Statistical Assumptions will be examined. For these analyses we will use simple measures of central tendency (means, medians, and mode) and variability (standard deviations). Means and standard deviations will be calculated for continuous variables and percentiles for categorical variables. Baseline Group Differences. ANOVA and Fisher Exact Test will be used to test for differences in baseline characteristics by groups and groups will be compared for equivalence of potentially confounding variables (such as age, rank and gender). Group inequities will be controlled in the analyses by using covariates or other appropriate statistical methods. Time Differences. Linear mixed effects regression models will be used to examine differences in time trends for the outcome variables among controls and those in the treatment groups. Random effects for subject will be included, and time will be examined. Our previous experience has been that for this type of intervention we find little variance explained by a random effect for time. The primary determination of group by time differences will use time as a continuous variable. In these regression analyses, the important primary measures will be expressed as a function of time, treatment group, and group-by-time interactions, while controlling for important covariates. Secondary analyses will include time as a factor to examine responses at individual time points.

Specific Aim I: To determine whether the treatment regimens are significantly more efficacious than standard HEP, using linear mixed effects models, as described above, we will estimate separate models for each of the following dependent variables: knee strength for flexion and extension, energy expenditure, time to complete a step down test, steps walked per day, distanced walked in 6 minutes, and number of times to complete the chair rise.

Specific Aim II: To determine whether the treatments improve QOL and symptoms of PFPS significantly more than HEP, using the same mixed effects method as with Specific Aim 1, we will estimate separate equations for PFPS pain symptom dependent variables. Primary independent variables will be treatment group, time, and group-by-time interaction.

Missing Data. Missing data rates and patterns will be assessed; in particular, missing data rates by treatment group will be examined. For the primary analysis, we will adjust for missing data by using an intent-to-treat analysis. All of the subjects in the study will be included in the analysis. Treatment effects will be compared on the basis of the subject's original group assignment. In addition to the traditional intention-to-treat analyses, we will assess patterns of change both within and between groups using the mixed effects regression models.

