Intervention: The rationale for the number of weeks of intervention and the number and timing of assessments is based on our previous work. NMES was found to increase strength after 36 sessions of training²². We will test participants at baseline, 3-weeks, 6-weeks, and 9-weeks when all outcome measures will be tested. Subjects in the NMES groups will have their percentage of MVC calculated to adjust the intensity of their NMES training. Information on pain status will be obtained at weekly checks, regardless of group assignment. The intervention weekly logs to determine pain and difficulty during home exercise, NMES and TENS will be reviewed and adjusted, as necessary. We will have weekly contact with participants during the 9 weeks of the study (baseline – week 9) either by in-person clinic visits, phone checks, text messaging or email.

The Control Home Exercise Program (HEP) Protocol: All participants will receive a standard home-based exercise rehabilitation protocol for PFPS. HEP teaches muscle strengthening exercises and self-management strategies to prevent recurrence. The HEP sessions provide the participant with a self-management framework for returning to duty following PFPS rehabilitation. During their baseline visit, participants will be provided a handout and given a demonstration of the daily exercises to be performed at home. A return demonstration by the participant will assure understanding. The exercises are quadriceps strengthening exercises. These exercises consist of stretching exercises of the quadriceps and hamstring muscles and a combination of open chain and closed chain exercises. The combined open and closed chain exercises are active straight leg raises, quadriceps straightening, step

up, and squats. At each study visit, participants will receive instructions on self-management strategies to prevent recurrence. The study coordinator will coordinate all study visits regardless of group assignment. Follow-up telephone calls will be made to remind participants of their visit and to control for individual contact made through phone calls to participants in the intervention group. To provide an attention control, the HEP only group will receive weekly communication from the study coordinator regarding compliance with the exercises. Delivery of the interventions for each arm of the study will be conducted independently, so there will be no cross-contamination between groups. The HEP group will receive a total of 62 sessions.

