To obtain a sample size of 136 adults with PFPS (34 per group), we will draw upon Active Duty members and Reserve/National Guard members on active duty status through the physical therapy clinic, family practice clinic and satellite clinics at BACH. All racial, ethnic, and gender groups will be recruited for the study. Active duty members who meet eligibility criteria and agree to participate in the study will be asked to participate.

The number of visits required for participants in all groups is 4, including 1 baseline visit, 2 visits for education and strength adjustments, and testing (weeks 3 and 6) and 1 9-week post-test assessment visit, for a total of 4 visits. The 3, 6, and 9-week visits will include strength adjustment, review of logs and abbreviated testing. Each standard BACH rehabilitation session will take 20 minutes, and each assessment (Weeks 3, 6, 9) approximately 1 hour and 10 minutes, with baseline testing 2 hour and 10 minutes; the total time over the 9 weeks will be approximately 5 hours and 45 minutes (Table 3).

Inclusion Criteria

The study will be open to all active duty personal who are:

- diagnosed with knee pain, categorized as anterior or retropatellar in one or both knees;
- self-reported difficulty performing at least two or more of the following activities associated with knee pain: prolonged sitting, stair climbing, running, jumping and repetitive movements such as kneeling or squatting or stooping;
- military service member at the time of diagnosis;
- age ≥ 18 and <45 years; and
- ability to provide freely given informed consent.

Exclusion Criteria

Those who might be at risk of adverse outcomes from the study interventions will be excluded. This includes individuals with

- Fracture or injury to external knee structures such that knee extension or flexion is impaired;
- A significant co-morbid medical condition (such as severe hypertension, neurological disorder or pacemaker/defibrillator) in which NMES strength training or unsupervised exercise is contraindicated and would pose a safety threat or impair ability to participate;
- Previous knee surgeries (i.e., tibiofemoral, patellofemoral) excluding knee arthroscopy;
- Knee instability or recurrent patella dislocation or subluxation;
- Inability or unwillingness to participate in a home exercise program or strengthening program;
- Inability to speak and/or read English;
- Reduced sensory perception in the lower extremities;
- Pregnancy;

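### The primary test compares slopes over time, but the SAP does not commit to a subject random slope, and a small past share of variance would not justify leaving it out

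*SAP*

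**What the plan says.** The SAP, Data Analysis (Time Differences), specifies linear mixed models in which "the important primary measures will be expressed as a function of time, treatment group, and group-by-time interactions", with covariates. It then says which form of time carries the conclusion: "The primary determination of group by time differences will use time as a continuous variable". The primary comparison is therefore between groups' linear slopes.

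On random effects there are two sentences. The first is "Random effects for subject will be included, and time will be examined". The second is "Our previous experience has been that for this type of intervention we find little variance explained by a random effect for time". No figure, outcome or study is attached to the second, and no criterion is attached to the first. Neither document names a covariance structure, a robust standard error or a degrees-of-freedom method.

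A further analysis is planned: "Secondary analyses will include time as a factor to examine responses at individual time points". Specific Aim II carries the method over, "using the same mixed effects method as with Specific Aim 1, we will estimate separate equations for PFPS pain symptom dependent variables".

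The Protocol (Methods, Intervention) fixes the schedule: "We will test participants at baseline, 3-weeks, 6-weeks, and 9-weeks when all outcome measures will be tested". Its Study population section gives 136 participants, 34 per group.

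**The concern.** When slopes are compared, between-subject variation in slope is part of the error. A model with only a random intercept spreads that variation across the residual and understates the standard error of the group-by-time contrast. Intervals are then too narrow and p-values too small, in every outcome model built this way.

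The only comment the SAP makes on a random time effect is that it explained little variance before. That measure can mislead. Where subjects differ a lot in level and the residual is small, slope variation can be a small share of total variance and still be large against the residual error of a slope. The share also changes with the coding of time, while the error of the contrast does not. With no retention rule, two analysts following this SAP could fit different error terms and report different primary p-values.

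**Working it through.** **Inputs from the documents.** Visits at 0, 3, 6 and 9 weeks; four groups of 34 (4 × 34 = 136, which agrees with the stated total). That total is the only design figure; it is not in dispute and cannot be derived further, since no alpha, power, effect size or SD is given.

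**Assumptions.** Two-sided 5%, a 1-df contrast of one arm with the exercise-only control, complete data, and intraclass correlation (ICC, the intercept's share of total variance) of 0.5, 0.7 or 0.8. Steps and energy expenditure come from a device worn daily (Protocol, Physical Activity Measures), so the figures apply to them only if they are summarised to the four visits.

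**Formula.** The mean of the visit times is 4.5, so the sum of squares is 4.5² + 1.5² + 1.5² + 4.5² = 45. Let σ² be the residual variance, τ² the slope variance and k = 45τ²/σ².

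- True variance of one subject's fitted slope: σ²/45 + τ².
- Variance implied by an intercept-only model: about σ²/45 + τ²/3, because the slope's sum of squares is spread over 3 within-subject degrees of freedom.
- Ratio, true to assumed: V = (1 + k)/(1 + k/3).
- Type I error: 2Φ(−1.96/√V). Standard error understated by 1 − 1/√V.

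**Without reference to time coding.** If the SD of subjects' true 9-week change is r residual SDs, then k = 45r²/81.

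| r | k | V | SE understated | Type I error, slope omitted |
|---|---|---|---|---|
| 0.25 | 0.035 | 1.023 | 1% | 5.3% |
| 0.5 | 0.139 | 1.088 | 4% | 6.0% |
| 1.0 | 0.556 | 1.312 | 13% | 8.7% |
| 1.5 | 1.250 | 1.588 | 21% | 12.0% |

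**By share of total variance.** For a slope share s, k = (45/m) × s/(1 − ICC − s), where m is the mean square of time: 45/4 = 11.25 if time is centred, (0 + 9 + 36 + 81)/4 = 31.5 if coded from baseline with an independent intercept. Example: s = 5%, ICC 0.7, centred gives k = 4 × 0.05/0.25 = 0.80, V = 1.80/1.267 = 1.42 and type I error 10.0%.

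| Share, coding | k at ICC 0.5 / 0.7 / 0.8 | Type I error, slope omitted |
|---|---|---|
| 1%, centred | 0.082 / 0.138 / 0.211 | 5.6 / 6.0 / 6.5% |
| 1%, from baseline | 0.029 / 0.049 / 0.075 | 5.2 / 5.4 / 5.6% |
| 5%, centred | 0.444 / 0.800 / 1.333 | 8.1 / 10.0 / 12.3% |
| 5%, from baseline | 0.159 / 0.286 / 0.476 | 6.2 / 7.0 / 8.2% |

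The same nominal share thus gives different error rates under the two codings. A raw-data simulation at ICC 0.7 and a 5% share (20,000 trials) gave 10.2% centred and 7.1% from baseline.

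**By how the slope is handled.** Simulated with 200,000 trials per scenario, true share 1–5%, ICC 0.5–0.8:

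- always keep the slope: 4.9–5.1%;
- keep it if a 5% F test of the slope variance is significant (132 and 272 df): 5.0–5.6% under either coding;
- drop it if its estimated share is below 5% (an illustrative threshold, not in the SAP): 5.6–9.3% centred, 5.0–6.4% from baseline.

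With zero slope variance, omission gives 4.9–5.1%.

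**The case against.** A reader might infer that the SAP excludes the random slope, or that its primary tests run at about 12%. The documents support neither. The SAP says time will be examined, which in context can well mean examining a random time effect. The remark on past experience states an expectation, not a rule. Harm needs slopes that vary, a decision to omit the random slope, and enough slope variance to matter.

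If examining means a formal test, most of the harm goes. The power of the 5% F test is P(F > c/(1 + k)) on 132 and 272 df, with c its critical value: about 79% at k = 0.444, 90% at k = 0.556 and 99% at k = 0.80. The large-inflation cases are therefore those a test would seldom miss. At k = 0.138 power is only about 22%, but omission there costs about one percentage point.

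The upper figures also depend on choices made here. The 12.3% needs centred time, ICC 0.8, a 5% share and outright omission; the 9.3% needs an invented threshold. At a 1% share, which fits the SAP's description more easily, the range is 5.2–6.5%. All of this stands and limits the size of the point.

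The time-as-factor analysis is not a full answer. It is secondary, and the SAP states no covariance structure for it, so it cannot be said either to repair the primary error term or to leave it unchanged.

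What remains is that the SAP does not fix the error term of its primary test, and the one consideration it mentions would not justify omitting the slope.

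**Conclusion.** The point holds as a cheap improvement to the specification. It does not show that the planned analysis is invalid, and it does not touch the sample size. The missing commitment is plain from the text; the consequence is conditional. Under the stated assumptions, omitting a slope that truly varies inflates pairwise type I error slightly at a 1% share and moderately at 5%. The ICC and the coding of time decide where in each range a given outcome falls, and the documents supply neither. A formal test largely removes the problem, and keeping the slope removes it.

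**What to change.** State in the SAP that every Aim I and Aim II group-by-time model includes a subject random intercept and a subject random slope for time, whatever the estimated slope variance. Name an unstructured covariance over the four visits as the fallback if the model does not converge. If the sponsor prefers a data-driven choice, prespecify a formal test of the slope variance and its level, not a share of variance explained.

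The cost is a sentence or two of SAP wording, with no change to design, sample size or conduct. If slopes truly do not vary, simulated intervals are about 0.5% wider (error taken from the slope mean square, 132 df) to 2.6% wider (slope variance bounded at zero). Occasional non-convergence is covered by the fallback.

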Study Protocol Document Cover Page

Official Title of the Study: Trial of Self-managed Approaches for Patellofemoral Pain Syndrome in Active Duty Military

NCT Number: NCT02597673

Date of Document: July 16, 2015

Trial of Self-managed Approaches for Patellofemoral Pain Syndrome in Active Duty

Objective

The overall objective of this project is to compare the three home-managed treatment regimens for PFPS: neuromuscular electrical stimulation (NMES), transcutaneous electrical nerve stimulation (TENS), and NMES combined with TENS to a standard home exercise program (HEP). Each of the three treatment arms will be supplemented by HEP and compared to a group receiving standard HEP alone. Our central hypothesis is that the combination of NMES with TENS will show significantly greater improvements in muscle strength, mobility, pain, daily activity and quality of life (QOL) than HEP alone.

Design

The Study will use a two-by-two factorial (NMES +/- and TENS +/-) design with repeated measures over time to compare the effects of NMES, TENS and combined NMES/ TENS on strength, mobility, symptoms, and QOL on military members with PFPS to the effects of a standard home exercise program. All groups will participate in the standard home exercise protocol. The groups will be assessed over 9 weeks to compare main and interactive effects over time. All groups will have an intensive 9-week program.

Participants will be randomly assigned to 1) NMES with the standard HEP protocol; 2) TENS with standard HEP protocol; 3) NMES and TENS with standard HEP protocol; and 4) standard HEP protocol alone (control group). We will not randomize participants until after the pre-treatment assessment has been completed. Participants will be familiarized with the test procedures prior to baseline testing, and then assessed again at 3, 6 and 9 weeks. The primary outcome measures are lower extremity muscle strength, physical activity, and mobility; and the secondary measures are symptoms/pain and QOL.

Methods

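### Baseline is measured before randomisation, but the primary mixed model gives each arm its own baseline level and leaves the covariates open; the slope test is valid but less precise than it could be

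*SAP*

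**What the plan says.** The Design section of the protocol sets the order of events: "We will not randomize participants until after the pre-treatment assessment has been completed". The Intervention paragraph under Methods gives the schedule: "We will test participants at baseline, 3-weeks, 6-weeks, and 9-weeks when all outcome measures will be tested". The planned size is 136, or 34 per arm.

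Under Time Differences, the SAP models the primary measures as "expressed as a function of time, treatment group, and group-by-time interactions, while controlling for important covariates", with a random effect for subject and time continuous in the primary test. It expects little from a random time effect: "Our previous experience has been that for this type of intervention we find little variance explained by a random effect for time". The time-as-factor model is secondary: "Secondary analyses will include time as a factor to examine responses at individual time points". Specific Aim II uses the same terms: "Primary independent variables will be treatment group, time, and group-by-time interaction".

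Under Baseline Group Differences, the SAP says "ANOVA and Fisher Exact Test will be used to test for differences in baseline characteristics by groups", and then "Group inequities will be controlled in the analyses by using covariates or other appropriate statistical methods". Age, rank and gender are given as examples. Neither document fixes the covariate list or the form of entry, names the baseline outcome as a covariate, or constrains the arms to a common baseline mean.

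**The concern.** When the outcome is measured before assignment, any baseline difference between arms is due to chance. With continuous time, a treatment-group main effect estimates those chance differences as four separate intercepts. The group-by-time estimate is unbiased over randomisations. In any one trial, though, a high baseline in one arm tends to be followed by values closer to the common mean, and the model reads part of that as a difference in trend. A common baseline mean removes this source of variance using data already collected.

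The SAP's remedy for imbalance does not address this. A covariate main effect shifts a person's whole profile up or down and leaves the slope alone. A covariate-by-time term can change the slope contrast, and the SAP leaves that choice open until after the baseline tests.

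**Working it through.** **Inputs from the documents.** Four arms of 34 (Study population; 4 × 34 = 136). Visits at weeks 0, 3, 6 and 9 (Intervention). Random intercept, continuous time, free group term (SAP, Time Differences).

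**Assumed inputs.** The within-person correlation r over 9 weeks is not given. The protocol's nearest figures are short-interval reliabilities: 0.97 to 0.99 for one-day strength retest, 0.94 for step-down, 0.917 for the 6-minute walk, and 0.95 over 2–3 days for the Kujala scale. These are upper guides to r. I use 0.5 to 0.94. Dropout is not stated either; 20% is an assumption. The documents give no power, alpha, effect size or SD, so there is no power figure to reproduce.

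**Step 1: variance of a slope contrast.** Mean visit time is 4.5 weeks; the sum of squares about it is 20.25 + 2.25 + 2.25 + 20.25 = 45. In units of the outcome SD:

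- Free baseline per arm (the SAP model): 2(1 − r) / (45n).
- Common baseline mean: 2 / {n[45/(1 − r) + 81/(1 + 3r)]}, where 81 = 4 × 4.5².
- Ratio, common over free: [45/(1 − r)] / [45/(1 − r) + 81/(1 + 3r)].

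At r = 0.7: 45/0.3 = 150 and 81/3.1 = 26.13, so the ratio is 150/176.13 = 0.852.

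| r | Ratio | Variance cut | Equivalent n per arm under the SAP model (34/ratio) | Cut with 20% dropout |
|---|---|---|---|---|
| 0.5 | 0.735 | 26% | 46 | 24% |
| 0.7 | 0.852 | 15% | 40 | 14% |
| 0.8 | 0.904 | 10% | 38 | 9% |
| 0.9 | 0.954 | 5% | 36 | 4% |
| 0.94 | 0.973 | 3% | 35 | – |

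Dropout is taken as monotone and spread evenly over the three follow-up visits. The ratios also apply to factorial main-effect slopes. If Fitbit data were analysed at ten weekly points (0 to 9), the cuts would be 18%, 9%, 6% and 3% at r = 0.5, 0.7, 0.8 and 0.9.

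**Step 2: time as a factor.** For the week-9 contrast, the ratio of baseline-adjusted to change-score variance is (1 − r²)/[2(1 − r)] = (1 + r)/2, that is 0.75, 0.85, 0.90 and 0.95 at r = 0.5, 0.7, 0.8 and 0.9.

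**Step 3: effect of one chance imbalance.** Under the SAP model, a baseline difference d moves the expected 9-week contrast by −9 × (4.5/45) × (1 − r)d = −0.9(1 − r)d. At r = 0.7 this is −0.27d. One standard error of the baseline difference is √(2/34) = 0.243 SD, giving a shift of 0.065 SD in absolute value. The standard error of the contrast is 9√[2 × 0.3/(45 × 34)] = 0.178 SD, so the shift is 0.37 SE. In general it is √[0.45(1 − r)] SE: 0.47, 0.37, 0.30 and 0.21 at r = 0.5, 0.7, 0.8 and 0.9.

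**Step 4: what covariates do.** With complete data, a covariate that is constant over time is orthogonal to the within-person slope, so its main effect cannot move the contrast. In 150 simulated trials (covariate explaining 13% of outcome variance, r = 0.7):

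- main effect, complete data: shift zero to machine precision;
- main effect, 20% dropout: mean shift 0.03 SE, maximum 0.16 SE;
- covariate by time, complete data, no true effect on slope: mean 0.06 SE, maximum 0.43 SE.

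**Step 5: validity.** In 4,000 simulated null trials per setting, the SAP slope test had type I error of 5.0% (r = 0.5) and 5.1% (r = 0.8).

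**The case against.** The strongest reply is that nothing is wrong. Time, group and group-by-time is a conventional model for comparing change, and its error rate is correct. That stands: this is a point about efficiency.

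The reliabilities in the protocol lie where the gain is only about 1–5%, and the 26% rests on an assumed correlation of 0.5. It is true that the size is unknown. But those figures come from retests over a day or a few days and do not settle a 9-week correlation, and under the stated model the constraint never increases the variance of the slope contrast.

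The sample-size equivalents assume a treatment effect linear from week 0. This also stands. At r = 0.5 and 0.7, the gain in signal-to-SE is 17% and 8% for a linear effect, 8% and 4% for one that starts after week 3, 3% and 1% for one seen only at week 9, and 37% and 19% for an early plateau. The size changes but the direction does not.

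The imbalance shifts in step 3 are not an extra bias. They restate the same loss conditionally on the observed baseline, and over randomisations the planned SE already covers them.

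Finally, the SAP does not say outright that baseline is one of the modelled responses, and its open covariate wording does not exclude the baseline outcome. I infer the former from the stated aim of comparing change over time and from the four test times. If something else is meant, the SAP should say so.

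**Conclusion.** The concern holds. The primary model ignores a baseline equality that the design guarantees in expectation, and so gives up precision in every group-by-time contrast. The loss is material at a within-person correlation of about 0.7 or below (15% of the variance at 0.7, 26% at 0.5) and slight at 0.9 or above (5% or less).

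These figures assume a random-intercept covariance, which the SAP's own remark on random time effects supports. With random slopes over an assumed range (SD of 9-week change 0.2 to 0.4 baseline SD, intercept–slope correlation −0.5 to 0.3, r from 0.5 to 0.9), the common-baseline model still has the smaller variance, with ratios from 0.61 to 0.998. The planned test's validity also assumes that the covariance model is right.

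Equality of baseline means applies only to outcomes completed before assignment. Fitbit baseline needs 3 days of wear, and the protocol does not say whether that falls before randomisation. The open covariate rule is the lesser part, mainly a gap in pre-specification. The change should be made, but it does not threaten the trial's conclusions.

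**What to change.** 1. Fit the primary mixed model with a common baseline mean: drop the group main effect and keep time and group-by-time. Apply the same constraint in the secondary time-as-factor model and in the Aim II models.
2. State that the 3-day Fitbit baseline wear is completed before assignment for the outcomes to which the constraint is applied.
3. If the baseline outcome is instead entered as a covariate with weeks 3–9 as responses, test the adjusted group difference (for example at week 9). The week 3–9 slope would miss any effect reached by week 3. Its variance is also 45/18 = 2.5 times that of the four-visit slope.
4. Report baseline data descriptively and do not use baseline tests to choose covariates. Name any covariates now (for example age and sex, already collected), state whether each enters as a main effect only or also by time, and use the same set in every model.

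The cost is SAP wording. No new data or visits are needed. Dropping the group main effect frees three parameters, and fixed covariates use a few degrees of freedom.
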